8.7.1.7 Treatment by interaction analysis

A center by treatment interaction will not be included in any of the analysis models.

8.7.1.8 Pooling of centers for analysis

Centers will be pooled by country depending on the distribution of randomized patients. The algorithm for the pooling of centers, if required, will be detailed in a separate document prior to unblinding.

8.7.2 Analysis of primary efficacy endpoint

The 400MW test used to calculate the 400MW gait speed will be performed at Screening, M3, M6/M9 and last assessment on treatment visits. The Screening value will be considered to be the baseline value. If the screening value is missing the baseline value will be considered as missing.

The main analysis of the primary endpoint (change from baseline to month 6 (M6)/month 9 (M9) in 400MW gait speed) will be performed using the FAS.

Change from baseline to M6/M9 in 400WM gait speed will be summarized by treatment group.

The main hypothesis to be tested in this study is the superiority of at least one dose of active versus placebo on the change from baseline in 400m gait speed after 6 months of treatment.

The null hypotheses H_{01} and H_{02} given below will be tested against the alternative hypotheses H_{A1} and H_{A2} respectively:

$$\begin{split} &H_{01}\!\!:\ \mu_1 - \mu_P \!<\! 0.1, \qquad H_{02}\!\!:\ \mu_2 - \mu_P \!<\! 0.1, \\ &H_{A1}\!\!:\ \mu_1 - \mu_P \geqslant 0.1, \qquad H_{A2}\!\!:\ \mu_2 - \mu_P \geqslant 0.1, \end{split}$$

Where μ_1 and μ_2 denote the mean change from baseline in meters per second in the 400MW gait speed at M6/M9 in the 175 mg BIO101 and 350 mg BIO101 groups. With μ_p denoting the mean change from baseline at M6/M9 in the placebo group. A minimum clinically significant benefit is set at 0.1 meter per second in the mean difference between groups (i.e., superiority margin).

A Mixed Effect Model Repeat Measurement (MMRM) model with fixed factors treatment and center and the baseline score and the stratification factor (gender) will produce an estimate of the contrast at M6/M9 in the change from baseline of the 400MW test gait speed between each active arm and the placebo group (section 8.7.1.1) (after adjustment by the Hochberg procedure (Section 8.7.1.6)).

The same MMRM model will be also fitted for the Per-Protocol population to give an estimand of the efficacy of 175mg BIO101 and 350mg BIO101 in the population with a good compliance to the protocol. The FAS is the main population/set of interest.

A by-subject listing of 400MW data will be provided.

Alternative methods to adjudicate missing data for the primary endpoint like the Bayesian Multiple Imputation (MI) methods will also be considered. Chen at al (2017) demonstrated the interest of applying Bayesian MI method to 400MW non-completers in the LIFE study⁹. More detail please refer to section 8.7.6.

Change from baseline to last assessment on treatment will be analyzed using an ANCOVA method as defined in Section 8.7.1.12, and will be performed using the FAS and Per-Protocol population separately.

Additionally, a responder analysis will be performed, using a logistic regression (method defined in section 8.7.1.3) to model 400MW gait speed test response at M6/M9. A responder is defined as an improvement (increase) of 0.1 m/s or more in 400MW gait speed test compared to baseline. A non-responder will be defined as a subject that is not a responder. Subjects with a missing value at the visit and/or missing baseline value will be considered as non-responders. The number and rate (%) of responders and non-responders will be provided by treatment group for the M3 and M6/M9 visits.

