A predefined subgroup efficacy analysis will also be performed on a number of pre-identified, at-high risk of worsening, subpopulations:

- Low gait speed
- Sarcopenic obesity
- Study participants with a chair stand sub-score of ≤2 of the SPPB
- Study participants who experience a deterioration in their ALM/BMI, as measured by the DEXA scan in the M6 visit and compared to the baseline measurement

Subgroup analyses will be provided through a forest-plot approach.

General Objectives:

- To evaluate the safety and efficacy of two doses of BIO101 (175 mg b.i.d. and 350 mg b.i.d.) orally administered for 26 weeks versus placebo in a population of community dwelling older men and women (aged ≥ 65 years) living at home and at risk of mobility disability.
- 2. To estimate treatment effect on improvement of physical function after a six-month treatment versus placebo in the target population.
- 3. To estimate treatment effect on reduced risk of mobility disability after a six-month treatment versus placebo in the target population.

Primary Objective:

 To evaluate the effect of two daily doses of BIO101 versus placebo on mobility function as measured by gait speed using the 400MW test. The absolute change from baseline in m/s observed in each treatment group at M6 will be compared to the placebo group. A minimum clinically significant benefit is set at 0.05 m/s in the mean difference between groups from M6

Objectives:

compared to baseline. The preliminary data from the SARA observational study (SARA-OBS) suggests that the untreated population naturally experienced a deterioration of 0.05 meter per second, when compared at M6 to baseline. Taken together, this increases the expected difference between treatment and placebo groups to 0.1 meter per second at M6 – corresponding to what is considered a clinically significant difference.

Key Secondary Objectives:

- a. To compare the change from baseline of a standardized patient reported outcome (PRO): the PF-10 sub-score of the SF-36. A minimum clinically significant benefit is set at 2-point difference of the change at M6 from baseline versus placebo in the mean difference between groups.
- b. To compare the change from baseline to month 6 of the muscle strength using the handgrip strength test. A minimum clinically significant benefit is set at 2 kg difference of the change at M6 from baseline versus placebo in the mean difference between groups.

Other Secondary Objectives:

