9 STATISTICAL CONSIDERATIONS

9.1 STATISTICAL HYPOTHESES

The main hypothesis to be tested in this study is the superiority of at least one dose of active versus placebo on the change from baseline of the 400 m gait speed criterion after 6 months of treatment.

In order to deal with the multiplicity issue due to the two doses, a Hochberg procedure will be used for testing the main hypothesis.

Full details of the analysis and the procedure will be given in the statistical analyses plan (SAP) of the study.

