9.2 SAMPLE SIZE DETERMINATION

Originally, the sample size was calculated for a comparison test at a 0.05 two-sided significance level, a power of 80%, to detect a difference of 0.05 m/s (minimal clinically important difference) between active groups and placebo on the change from baseline in the 400 m gait speed at 6 months, with a standard deviation of 0.13 (estimated from the VIVE2 trial, Fielding et al, 2017⁶²).

After analysis of the preliminary data from our observational trial data (SARA-OBS, with approx. 105 completers), the following were learned:

- During the 6 months follow-up, this study population deteriorated as suggested by a decreased gait speed of 0.05 meter per second on the 400MW test, with a standard deviation of the change from baseline of 0.2
- The expected effect of BIO101 remains at 0.05 meter per second, as the change from baseline
- Together, this new information allows an increase of up to 0.1 m/s to be considered as a minimal clinically important difference of changes at the M6 visit from baseline between the treatment groups. Under these assumptions, a number of 64 patients/group is needed, giving a new sample-size of 192 patients for 3 arms, with a standard deviation of 0.20 (estimated from SARA-OBS preliminary data).

Taking into consideration this increased expected difference between treatment arms, a formal interim analysis will be performed by the DSMB when half subjects reach their month 6 visit (See section 9.4.6). Once half study participants complete their End-of intervention study visit, an unblinded 'promising zone' interim analysis will take place and determine if there is a need to increase the sample size based on the complete efficacy data.

Based on current calculation and given a limited 20% provision for premature withdrawals or lost-to-follow up, a total number of 231 participants will be included in the study.

It is expected, that due to COVID-19 related restrictions, that the number of non-evaluable withdrawals will be higher than 20%. However, reassessment of the sample size, will take place, as a part of the interim analysis, that will take place after restrictions are lifted.

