8 STATISTICAL METHODS

8.1 General statistical conventions

All statistical procedures will be completed using SAS® version 9.3 or higher.

Unless otherwise stated, all statistical testing will be two-sided and will be performed using a significance (alpha) level of 0.05. Two-sided 95% confidence intervals (CI) will be provided for the difference between treatment groups.

Descriptive statistics (mean, standard deviation, 95% confidence interval for mean, minimum, median, maximum, and number of observations and missing cases) will be used for quantitative variables. Frequencies and percentages will be used for categorical variables. The summaries will be presented by treatment group, unless otherwise specified. Percentages will be rounded to one decimal place.

Unless stated otherwise, unscheduled data will not be included in the summaries or analysis.

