8.7.1.6 Multiplicity

To strictly control overall type I error rate for the analysis of the primary and the key secondary endpoints to a two-sided 5% level, a Hochberg procedure will be used.

The aim of the study is to show that at least one dose is statistically superior to placebo while the family-wise type I error rate is maintained at the two-sided $\alpha = 0.5$ for the following primary and key secondary endpoints.

- Change from baseline to month 6 (M6)/ month 9 (M9) in 400MW gait speed
- Change from baseline to M6/M9 in Physical Function Domain (PF-10) sub-score of the Short Form Health Survey (SF-36)
- Change from baseline to M6/M9 in Handgrip strength test

The null hypotheses H_{01} and H_{02} given below will be tested against the alternative hypotheses H_{A1} and H_{A2} associated with the 175 mg BIO101 and 350 mg BIO101 groups respectively:

Where μ_1 and μ_2 denote the mean change from baseline at M6/M9 in the 175 mg BIO101 and 350 mg BIO101 groups. With μ_p denoting the mean change from baseline at M6/M9 in the placebo group.

A statistical rejection of H_{01} (or H_{02}) will indicate that the 175 mg BIO101 (or 350 mg BIO101) is superior to placebo or we say that the 175 mg BIO101 (or 350 mg BIO101) is significantly better than placebo. When at least one dose is significantly better than placebo, we say that the study is positive.

Two-sided p-values for comparing the 175 mg BIO101 to placebo and comparing the 350 mg BIO101 to placebo are denoted by p_{01} and p_{02} , respectively. The first step is to compare max (p_{01} , p_{02}) to 0.05. If max (p_{01} , p_{02}) \leq 0.05, both doses are claimed to be statistically better than placebo. If max (p_{01} , p_{02})> 0.05, the second step is needed to compare min (p_{01} , p_{02}) to 0.5/2 =0.025. If min (p_{01} , p_{02}) \leq 0.025 at the second step, the dose with is concluded to be statistically better than placebo. Otherwise no dose can be claimed to be better than placebo.

Multiplicity concerns for the non-key secondary endpoints are kept under control by the prespecification of key-secondary endpoints and a low number of secondary endpoints and analyses. Analysis of the non-key secondary endpoints will be considered supportive and no adjustments for multiplicity will be made.

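### The SAP's primary null hypothesis carries a 0.1 m/s margin equal to the effect the trial is sized to detect against zero, so the test as written has about 2.5% power rather than 80%

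*SAP*

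**What the plan says.** SAP 8.7.2 first describes the main hypothesis as superiority of at least one dose over placebo. It then displays H0 as an active-minus-placebo difference in mean change below 0.1 m/s and HA as a difference of at least 0.1 m/s, for each dose. The text under the display confirms that the number is meant as a margin: "A minimum clinically significant benefit is set at 0.1 meter per second in the mean difference between groups (i.e., superiority margin".

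The rest of the plan reads differently:

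- Protocol 9.1 states the hypothesis as "superiority of at least one dose of active versus placebo on the change from baseline of the 400 m gait speed criterion", with no margin.
- Protocol 9.2 bases the revised sample size on a 0.1 m/s difference between groups and concludes that "a number of 64 patients/group is needed, giving a new sample-size of 192 patients for 3 arms, with a standard deviation of 0.20".
- SAP 8.7.1.6 applies Hochberg to the two-sided p-values comparing each dose with placebo. On a rejection, "we say that the 175 mg BIO101 (or 350 mg BIO101) is significantly better than placebo".
- SAP 8.7.1.1 reports the LS mean difference, its 95% CI and a p-value for the treatment difference. No shift by 0.1 is described.
- The SAP's list of changes from the protocol does not mention a margin.

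The role of 0.1 m/s also varies. The protocol synopsis says "A minimum clinically significant benefit is set at 0.05 m/s in the mean difference between groups from M6" compared with baseline and treats 0.1 as the expected difference. Protocol sections 3 and 8.1 and SAP 8.7.2 make 0.1 the minimum benefit. Protocol 9.2 uses it as both. SAP section 5 still carries only 0.05.

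**The concern.** A trial sized to detect 0.1 m/s against zero cannot also be expected to show that the effect exceeds 0.1 m/s. If the written hypotheses govern, a drug that performs exactly as assumed fails almost every time. If a test of zero is run instead, a positive result does not reject the null hypothesis that the SAP states.

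The two readings are different questions put to the same data, and a signed SAP that supports both leaves the primary verdict to whichever sentence is followed. The same ambiguity reaches the interim rule in Protocol 9.4.7, which defines conditional power as the chance of rejecting the null hypothesis at the final analysis.

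**Working it through.** **Inputs**

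- Difference 0.1 m/s (Protocol 9.2: the new information "allows an increase of up to 0.1 m/s to be considered as a minimal clinically important difference of changes at the M6 visit").
- SD 0.20 and 64 per arm (Protocol 9.2).
- Two-sided 5% and 80% power. Protocol 9.2 gives these for its original calculation: "the sample size was calculated for a comparison test at a 0.05 two-sided significance level, a power of 80"%. The revised calculation states no new values. SAP 8.1 confirms that "all statistical testing will be two-sided and will be performed using a significance (alpha) level of 0.05".
- Margin 0.1 m/s (SAP 8.7.2).

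**Reproducing the 64 per arm (null = 0)**

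Normal approximation: n = 2 × (1.96 + 0.8416)² × 0.20² / 0.1² = 62.8, so 63. The exact two-sample t-test gives 79.5% power at 63 and 80.1% at 64, so 64 per arm. The plan's figure reproduces, and it does so against a null of zero.

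**Power against the written null (null = 0.1)**

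SE = 0.20 × √(2/64) = 0.0354 m/s.

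Power = 1 − Φ(1.96 − (true difference − 0.1)/SE).

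| True difference (m/s) | (true − 0.1)/SE | Power, null at 0.1 |
|---|---|---|
| 0.10 | 0 | 2.5% |
| 0.15 | 1.414 | 29% |
| 0.20 | 2.828 | 81% |

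Against zero, a true difference of 0.10 gives 0.1/0.0354 = 2.828 and hence 81% by the same normal formula (80.1% by the t-test).

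At a true difference of 0.10 the 2.5% does not depend on sample size or SD, because 0.10 is the boundary of the null. At 77 per arm it is still 2.5%.

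**Observed difference needed to reject (single comparison)**

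- Null at zero: 1.96 × 0.0354 = 0.069 m/s.
- Null at 0.1: 0.1 + 0.069 = 0.169 m/s.

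An estimate between these two values, which includes the assumed 0.10, succeeds on one reading and fails on the other.

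**With Hochberg** (500,000 simulated trials, shared placebo arm, both doses truly at 0.1 m/s)

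| Null | At least one dose | A given dose |
|---|---|---|
| 0 | 87% | 79% |
| 0.1 | 2.4% | 1.4% |

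**Sample size if a margin were intended**

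For 80% power at a true difference of 0.15: n = 2 × (1.96 + 0.8416)² × 0.20² / 0.05² ≈ 251.2, so 252 per arm.

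**The case against.** The strongest reply is that the analysis actually run will almost certainly test zero. SAP 8.7.1.1 and 8.7.1.6 speak of p-values for the difference from placebo and describe no offset. They fix the claim as better than placebo, not at least 0.1 m/s better. On that view the display in 8.7.2 is a drafting slip beside an analysis with about 80% power, and the reported CI lets any reader compare the result with 0.1.

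Much of this stands. The 2.5% applies if the written hypotheses govern, and it is not a forecast for the program that will be run. The code offers only partial support either way. The ANCOVA contrasts in Appendix A and the multiple-imputation example in Appendix S2 contain no 0.1 offset, but the MMRM code for the main analysis and the hypothesis display in 8.7.1.6 are not in the text available.

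What does not stand is that the slip is harmless. The margin appears in both hypotheses and is named in the prose, for the primary endpoint, and nothing elsewhere corrects it. It is either an undeclared change to the primary hypothesis or an error, and both call for correction.

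The 0.05 versus 0.1 labelling is a separate and smaller inconsistency. The synopsis explains where the numbers come from: 0.05 of benefit plus 0.05 of natural decline.

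**Conclusion.** The concern holds. The primary hypotheses in SAP 8.7.2 contradict Protocol 9.1, the sizing in Protocol 9.2 and the decision rule in SAP 8.7.1.6. Taken as written, they reduce power at the assumed effect from about 80% to 2.5% per dose, and a true difference of about 0.20 m/s would be needed to regain 80%.

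The figures assume SD 0.20, 64 evaluable patients per arm and two-sided 5% (one-sided 2.5% for the margin test), before the Hochberg step. A one-sided 5% reading would give 5% instead of 2.5%, which does not change the conclusion. The 80% target is stated only for the protocol's original calculation, but it reproduces the revised 64 per arm.

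**What to change.** In SAP 8.7.2:

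- Replace the hypotheses with H0: μ_active − μ_placebo = 0 against a two-sided alternative for each dose, with superiority claimed only when the estimate favours BIO101.
- Delete the parenthesis that calls 0.1 m/s a superiority margin.
- Keep 0.1 m/s as the difference assumed for sizing and as a benchmark for reading the estimate and its CI.

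Check that the hypothesis display in SAP 8.7.1.6, the MMRM code and the separate interim-analysis SAP use the same null.

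Give 0.05 and 0.1 m/s one label each across the protocol synopsis, sections 3, 8.1 and 9.2, and SAP sections 5 and 8.7.2.

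If a margin test really is intended, the SAP must say so, list it as a change from the protocol, and justify a trial with 2.5% power at its own assumed effect.

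The cost is a text amendment before unblinding, with no added patients or data. Power at 64 per arm is then about 80% per comparison, as planned.

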8.7.3 Analysis of secondary efficacy endpoints

8.7.3.1 Analysis of key secondary efficacy endpoints

The key secondary endpoints (change from baseline to M6/M9 in Physical Function Domain (PF-10) and change from baseline to M6/M9 in Handgrip strength test) will be summarized by treatment group and analyzed using the FAS. With sensitivity analysis performed using the PP population. The FAS is the main population/analysis set of interest.

Details of how to calculate PF-10 from the SF-36 questionnaire is in Appendix B - Short Physical Performance Battery (SPPB)

Summary performance score: Each of the three performance measured is assigned a score ranging from 0 to 4, with 4 indicating the highest level of performance and 0 the inability to complete the test. For the test of balance, participants are assigned a score of 1 if they can hold a side-by-side standing position for 10 seconds but are unable to hold a semi-tandem position for 10 seconds; a score of 2 is assigned if they can hold a semi-tandem position for 10 seconds; a full-tandem position for 3 seconds; a score of 3 is assigned if they can stand in a full-tandem position for 3 seconds; a score of 4 is assigned if they can stand in a full tandem position for 10 seconds.

Four categories are computed for walking speed and chair stands, according to cut-off points that are based on quartiles of the time to perform each task assessed in the EPESE. The time of the faster of two walks is scored as follows: > 8.7 sec = 1; 6.21 to 8.70 sec = 2; 4.82 to 6.20 sec = 3; < 4.82 sec = 4; a score of 0 is assigned to participants unable to perform the test. The time required to perform five chair stands is scored as follows: $\ge 16.70 \text{ sec} = 1$; 13.70 to 16.69 sec = 2; 11.20 to 13.69 sec = 3; $\le 11.19 = 4$. A score of 0 is assigned to participants unable to perform the task. A summary score ranging from 0 (worst performers) to 12 (best performers) is calculated by adding subscores from the walking speed, chair stands and balance tests.

Appendix C.

The handgrip strength test will be performed at Day 0 and at the M6/M9 visit or the end-ofintervention visit and will be measured 3 times for both hands. Grip strength is considered as the dominant hand so the highest of all 3 attempts for the dominant hand will be used for the analysis. The highest value for each hand will be summarized by treatment group. If there has been current flare-up of pain or has undergone fusion, arthroplasty, tendon repair, synovectomy, or other related surgery for the dominant hand or wrist in the past 3 months, the other hand will be tested. For the handgrip strength test, a minimum clinically significant benefit is set at 2 kg difference in the change at M6/M9 from baseline versus placebo in the mean difference between treatment groups.

Fatigue strength will be summarized by treatment group.

The analysis of change from baseline to M6/M9 in Physical Function Domain (PF-10) will use the same method as for analysis of the primary efficacy endpoint as detailed in section 8.7.1.1.

Missing data will not be replaced in these analyses but the MMRM model on observed data is known to perform well under a MAR hypothesis.

An ANCOVA method detailed in section 8.7.1.12 will be used to analyse change from baseline to M6/M9 in Handgrip strength test.

Alternative methods to adjudicate missing data for the primary endpoint like the Bayesian Multiple Imputation (MI) methods will also be considered for Physical Function Domain (PF-10). Chen at al (2017) demonstrated the interest of applying Bayesian MI method to 400MW non-completers in the LIFE study⁹. More detail please refer to section 8.7.6.

A responder analysis will be performed, using a logistic regression (method defined in section 8.7.1.33) to model PF-10 response at M6/M9. A responder is defined as an improvement of PF-10 greater or equal to 2 points compared to the baseline value, at an individual level. A non-responder for a visit (M3 or M6/M9) will be defined as a subject that is not a responder at that visit. Subjects with a missing value at a visit (M3 or M6/M9) will be considered as non-responders. The number and rate (%) of responders and non-responders will be provided by treatment group for the M3 and M6/M9 visits.

Handgrip strength test will be summarized and analyzed in the same way as PF-10 response. Where response is defined as ≥ 2 kg improvement in handgrip strength test at M6/M9 compared to the baseline value, at an individual level. A non-responder is a subject that is not a responder. Subjects with a missing value at M6/M9 will be considered as non-responders. The number and rate (%) of responders and non-responders will be provided by treatment group.

A by-subject listing of PF-10 and Handgrip strength test will be provided.

Page 36 of 69

